9.7.3 Statistical Methods

All endpoints will be presented by descriptive statistics for baseline, 12-months, and End of Study assessments. Assessments done at 6-months and 18-months will be presented similarly. Quantitative (continuous) variables will be summarized with the use of descriptive statistical measures [mean value, standard deviation (SD), median, min-max, Q1-Q3]. Qualitative (categorical) variables will be displayed as frequencies and percentages (N, %).

The normality of distributions will be examined using the Shapiro-Wilk test in order to determine whether or not to use parametric methods for analysis.

Primary Endpoint: Pre- and post- baseline ARR will be compared by ANOVA or Wilcoxon signed-rank test if data is not normally distributed. The 95% Confidence Interval (CI) for the difference will be presented.

If appropriate, sensitivity analyses will be done to determine the impact of confounding factors or to describe the outcome for special subject groups fulfilling predefined criteria. Details will be described in the SAP.

For **Secondary and exploratory endpoints** the following calculations and comparisons will be performed:

- Pre- and post- baseline ARR (1 year) will be compared by ANOVA or Wilcoxon signed-rank test if data is not normally distributed. The 95% Confidence Interval (CI) for the difference will be presented.
- For all other secondary endpoints, 95% CI will be calculated for the result at each timepoint and for the differences whenever applicable, using appropriate methods.

In the analysis of 6-month disability progression/improvement EDSS, T25FW and 9-HPT values must be obtained at sequential time points, separated by 6-month intervals. As T25FW and 9-HPT are optional and will be performed if done as per routine practice, missing values may occur and could lead to bias in their analysis. Methods to handle this bias issue will be described in detail in SAP.

A subgroup analysis will be conducted on effectiveness endpoints (ARR at 1 and 2 years, percentage of patients with 6-month disability progression and improvement), with 5 groups defined according to the pre-baseline DMD treatment (IFN- B 1a / IFN- B 1 B / Glatiramer Acetate, Teriflunomide, DMF).

CCI			

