# 14.3.1 Secondary Objective: Derivation and analysis of the Secondary Outcome 6-month Disability Progression

#### **Derivations**

Disability progression will be assessed using the Visit 4 data and comparing the results with Visit 3. As per definition, if Visit 4 and Visit 3 dates are not separated by at least 24 weeks, disability progression will be set to missing. Disability progression will be assessed if at least one assessment (EDSS, T25FW or 9HPT) is available. As per definition, disability progression will be derived as "Yes" if at least one of the below cases occur:

- Visit 4 EDSS is ≥1 point greater than Visit 3 EDSS if Visit 3 EDSS is greater than 0;
- Visit 4 EDSS is 1.5 or greater when Visit 3 EDSS is 0;
- 20% increase in the T25FW score (average of the two trials) from Visit 3 to Visit 4;
- 20% increase in the 9HPT score (The two trials for each hand are averaged, converted to the reciprocals of the mean times for each hand and then the two reciprocals are averaged) from Visit 3 to Visit 4.

If none of those cases occurred, disability progression will be set to "No".

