# 14.4.1 Secondary Objective: Derivation and analysis of the Secondary Outcome 6-month Disability Improvement

#### **Derivations**

Disability improvement will be assessed using the Visit 4 data and comparing the results with Visit 3. As per definition, if Visit 4 and Visit 3 dates are not separated by at least 24 weeks, disability improvement will be set to missing. Disability improvement will be assessed if at least one assessment (EDSS, T25FW or 9HPT) is available. As per definition, disability improvement will be derived as "Yes" if at least one of the below cases occur:

- Visit 4 EDSS is ≥1 point smaller than Visit 3 EDSS if Visit 3 EDSS is greater than 1.5;
- Visit 4 EDSS is 0 when Visit 3 EDSS is 1.5;
- 20% decrease in the T25FW score (average of the two trials) from Visit 3 to Visit 4;
- 20% decrease in the 9HPT score (The two trials for each hand are averaged, converted to the reciprocals of the mean times for each hand and then the two reciprocals are averaged) from Visit 3 to Visit 4.

If none of those cases occurred, disability improvement will be set to "No".

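### The disability derivation does not require the same test at both compared visits, so applied as written it codes some patients with no measured change as 'No'

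*SAP*

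**What the plan says.** SAP 14.3.1 sets the task as a comparison of two visits: "Disability progression will be assessed using the Visit 4 data and comparing the results with Visit 3". Three rules then decide the outcome.

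- **Spacing:** "if Visit 4 and Visit 3 dates are not separated by at least 24 weeks, disability progression will be set to missing". This concerns visit dates, not test values.
- **Availability:** "Disability progression will be assessed if at least one assessment (EDSS, T25FW or 9HPT) is available". No visit is named.
- **Default:** "If none of those cases occurred, disability progression will be set to" 'No'. There is no exception for a change that cannot be computed.

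All four 'Yes' criteria (two for EDSS, one each for T25FW and 9HPT) are Visit 3 to Visit 4 changes.

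SAP 14.4.1 has the same structure for improvement: "Disability improvement will be assessed if at least one assessment (EDSS, T25FW or 9HPT) is available", followed by "If none of those cases occurred, disability improvement will be set to" 'No'. The same derivation is carried to Visits 1 to 3 for progression and Visits 2 and 3 for improvement. Appendix 18.2 lists both outcomes, limited to Visit 2, among the interim outputs.

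Protocol 9.7.3 says that "EDSS, T25FW and 9-HPT values must be obtained at sequential time points, separated by 6-month intervals", which implies a pair. It also expects missing values for the two optional tests. Both SAP sections say that nothing will be imputed in the main analysis.

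**The concern.** Every 'Yes' criterion needs the same component at two visits, while the availability rule needs only one value. A patient can therefore qualify for assessment, be unable to meet any criterion, and fall through to 'No'. That 'No' records an absence of change that nobody observed, which is in effect an imputation in an analysis said to have none.

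Two secondary percentages and their exact intervals are at stake. A false 'No' lowers the progression percentage, which favours the product, and lowers the improvement percentage, which works against it. Such patients can occur because assessments follow routine care and T25FW and 9HPT are optional. SAP 10.2.1 does not treat departures from the assessment schedule as important deviations, so a skipped test would not be flagged by that route.

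**Working it through.** The plan states no figure for this point, so there is nothing to reproduce. The check has three steps.

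**1. Which availability patterns are affected.** Each of the three components is in one of four states: measured at neither visit, Visit 3 only, Visit 4 only, or both. That gives 4³ = 64 patterns. Patterns with no component at both visits: 3³ = 27. One of these has no value at all and fails the availability rule. The other 27 − 1 = 26 pass it, can never be 'Yes', and become 'No', provided the spacing rule is met. These are counts of patterns, not of patients, and say nothing about frequency.

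Examples, with 9HPT absent throughout and visits at least 24 weeks apart:

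| EDSS V3 | EDSS V4 | T25FW V3 | T25FW V4 | Result as written |
|---|---|---|---|---|
| 2.0 | 3.5 | – | – | Yes (paired, change 1.5) |
| – | 3.5 | – | – | No (no pair) |
| 2.0 | – | – | 5.0 | No (no pair) |
| – | – | – | – | Not assessed |

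**2. Which denominator applies.** The SAP points two ways.

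- Section 9 bases proportions on the analysis set unless stated otherwise, keeping missing observations in the denominator as their own category. On that rule, moving a patient from 'No' to missing changes neither the numerator nor n.
- Section 14.3.2 says the complete-case analysis, which sets undetermined cases to missing, will include fewer patients than the main analysis. Section 14.4.2 expects the complete-case version to overestimate the improvement effect. Turning 'No' into missing can raise a percentage only if missing patients leave the denominator.

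**3. Size under an evaluable-patient denominator.** Let p be the percentage among patients with a pair and u the share of otherwise-assessed patients without one. Then reported percentage = p × (1 − u).

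The documents give neither p nor u, so both are assumed. N = 242 (Protocol 9.5) is used only for scale, as if every enrolled patient passed the spacing and availability rules. Counts are rounded to whole patients; intervals are 95% Clopper-Pearson.

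| Assumed p | Assumed u | Pair required | Default 'No' |
|---|---|---|---|
| 10% | 5% | 23/230 = 10.0% (6.4–14.6) | 23/242 = 9.5% (6.1–13.9) |
| 10% | 10% | 22/218 = 10.1% (6.4–14.9) | 22/242 = 9.1% (5.8–13.4) |
| 10% | 20% | 19/194 = 9.8% (6.0–14.9) | 19/242 = 7.9% (4.8–12.0) |
| 10% | 30% | 17/169 = 10.1% (6.0–15.6) | 17/242 = 7.0% (4.1–11.0) |
| 20% | 30% | 34/169 = 20.1% (14.4–27.0) | 34/242 = 14.0% (9.9–19.1) |

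The interval also narrows, because unmeasured patients count in n.

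**The case against.** The strongest reply is that the text already means a pair. The availability sentence belongs to a rule about comparing two visits. Section 14.3.2 counts three assessments, not six values, so an available assessment can be read as a component that can be evaluated. The same section recognises patients whose progression cannot be assessed as distinct from 'No', and its fourth analysis speaks of both EDSS scores. The no-imputation statement and Protocol 9.7.3 point the same way. This reading is plausible and probably intended. It is still not written, and a programmer who follows the sentence as it stands gets a different result.

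Second, EDSS is scheduled at all five visits and is not optional. If it is recorded at both compared visits, missing T25FW or 9HPT values cannot cause the problem. This stands, and it may keep u small.

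Third, sensitivity analyses 1 and 2 for progression recode a 'No' reached without all three assessments, to missing and to 'Yes' respectively. This limits the damage but leaves the main estimate as it is. If availability is read in the same loose way, a patient with all three tests at Visit 4 and none at Visit 3 still counts as 'No'. For improvement, the second analysis assigns 'No' anyway. The EDSS-only analysis states no pair rule.

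A reader might go further and infer that everyone who does not meet a criterion becomes 'No'. The documents do not support that: visits under 24 weeks apart give missing, and a patient with no value is not assessed. A patient lacking either visit has no pair of dates with which to meet the spacing rule, although the SAP does not spell this case out.

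**Conclusion.** The point holds as a defect in a stated rule with a narrow reach. It affects only patients whose compared visits are at least 24 weeks apart and who have some value but no component at both. As written, they are coded 'No' for progression and for improvement without a measured change.

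The consequence depends on the denominator. With evaluable patients, as 14.3.2 and 14.4.2 imply, both percentages are diluted by (1 − u) and their intervals are too narrow. Under the general rule in section 9, the 'Yes' percentage and its interval do not move, but unmeasured patients are displayed as 'No' instead of missing.

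It would be tempting to conclude that the plan demonstrably understates progression by a known amount, or that it means to count unmeasured patients as non-progressors. Neither follows. The documents give no figure for u, the 5% to 30% range is assumed, and the surrounding text suggests the opposite intention. The outcomes are secondary and descriptive and the primary relapse analysis is untouched, but the correction should be made because two programmers could reach different results from the same sentence.

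**What to change.** In SAP 14.3.1 and 14.4.1:

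- Replace the availability sentence with: *assessed if at least one component (EDSS, T25FW or 9HPT) is available at both visits being compared; otherwise set to missing*.
- Allow 'No' only when at least one paired component was evaluated.
- Apply the same condition to the EDSS-only sensitivity analysis and to the earlier visits that are reported.
- Report how many patients are set to missing for this reason.
- State that the percentage and its Clopper-Pearson interval use patients with an evaluable outcome, as an explicit exception to the general rule in SAP section 9. Without this, the pair condition would leave the reported percentage unchanged under that rule.

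The cost is a few sentences in two sections and one condition in the program. The downside is slightly fewer evaluable patients and slightly wider intervals.

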8.2 Secondary Objectives

- To assess change in annualized relapse rate (ARR) in patients switching from first-line DMDs to Cladribine tablets, between the 12-month pre-baseline period and over the 12 months period after initiation of Cladribine tablets (1 year)
- To assess disability progression. Disability progression is defined as progression on ≥1 of 3 components (EDSS, T25FW, and/or 9HPT) confirmed ≥24 weeks apart and with a ≥20% minimum threshold change for T25FW and 9HPT. T25FW and 9HPT are optional and will be performed if done as per routine practice. Progression on EDSS is defined as at least 1 point in the EDSS score or an increase of at least 1.5 points if the baseline EDSS score is 0.
- To assess disability improvement. Disability Improvement is defined as improvement on ≥1 of 3 components (EDSS, T25FW, and/or 9HPT) confirmed ≥24 weeks apart and with a ≥20% minimum threshold change for T25FW and 9HPT. T25FW and 9HPT are optional and will be performed if done as per routine practice. Improvement on EDSS is defined as a decrease in EDSS by at least 1 point (1.5 points if baseline EDSS was 1.5).
- To assess safety of Cladribine tablets in the real world, at two years
- To assess Quality of Life and treatment satisfaction
- To assess treatment adherence

-

Exploratory Objectives

- For those patients that the treating physicians decide to prescribe an MRI at baseline and/or Year 2:
 - 1. To compare MRI characteristics between baseline and Years 1 and 2
 - To compare MRI characteristics between the 12-month pre-baseline and postbaseline results (Years 1 and 2)
- To study effectiveness in 5 subgroups, defined according to the pre-baseline DMD treatment (IFN- B 1a / IFN- B 1 B / Glatiramer Acetate, Teriflunomide, DMF).

L04AA40 MS700568_0070	Cladribine	
9	Research Methods	
9.1	Study Design	
9.1.1	Design Overview	

This is a prospective, non-interventional, multicenter, Phase IV study in patients with a confirmed diagnosis of RRMS who switched from first-line DMD treatment (Interferons, Glatiramer Acetate, Teriflunomide, DMF) to treatment with Cladribine tablets in routine clinical practice.

No study specific interventions will be performed on the patients and there will not be any study specified visits. Assessments planned in this protocol will be according to clinical practice.

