9.3 Variables

- Demographic data: Gender, age, race (if allowed as per local regulation)
- Other Baseline Assessments: Weight
- Medical history, including MS, malignancies, severe and opportunistic infections
- MS-Medication history: DMD, immunosuppressive/immunomodulatory agents (other than DMD, such as corticosteroid treatment)
- Therapy with Cladribine Tablets [date of administration and number of tablets taken versus prescribed dose (treatment adherence)]
- Reason for switching from first line DMD to Cladribine Tablets
- Participation in a Cladribine Patient Support Program
- Course of disease
 - o Relapses
 - o MRI data
 - T2, T1 Gd+ and CUA lesion counts
 - o EDSS Score
 - o T25FW (time in seconds, optional)
 - o 9-HPT (time in seconds, optional)
- TSQM-v1.4 VAS score
- MSIS-29 score

- · EQ-5D-3L score
- Safety (Serious Adverse Events (SAEs), Adverse Events of Special Interest (AESI) and Adverse Drug Reactions (ADRs))

Derived and transformed data needed for the analysis are described in Section 9.7.2.

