#### **Analysis methods**

No missing data imputation will be performed. The proportion of patients with 6-month disability progression at the end of study will be presented including associated 95% Clopper Pearson exact intervals.

Disability progression at Visit 1, Visit 2 and Visit 3 will also be presented and derived in the same way. A bar plot with disability progression from Visit 1 to Visit 4 will be presented. Additionally, the results for EDSS, 9HPT and T25FW scores will be presented descriptively by Visit, including an absolute and relative change from baseline and to the previous visit.

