## 14.3.2 Sensitivity Analyses of the Secondary Outcome 6-month Disability Progression

Four sensitivity analyses will be performed to assess the robustness of the results of the secondary outcome.

The first sensitivity analysis will be a complete case analysis that will derive disability progression only for cases where it can be determined without reservations, setting all the other cases to missing. This means that if only one or two out of the three assessments are available, disability progression will either be "Yes" if those are sufficient for the assessment or "Missing" if progression criteria are not observed in any of the available assessments. The number of patients included in these analyses will be less than the ones includes in the main analysis.

The second sensitivity analysis will include a Non-responder (NR) missing data imputation. All patients for which disability progression cannot be assessed or is "No" but not all three assessments are available will be set to "Yes".

Both approaches will provide a significant underestimation of the treatment effect due to the anticipated missing data in the optional assessments.

A third sensitivity analysis will be performed using EDSS only for disability assessment derivation.

The fourth sensitivity analysis will replicate the above described third sensitivity analysis but by two subgroups:

- Patients with at least one EDSS score obtained within 3 months following a relapse
- Patients with both EDSS scores obtained more than 3 months following a relapse

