#### **Analysis methods**

No missing data imputation will be performed. The proportion of patients with 6-month disability improvement at the end of study will be presented including associated 95% Clopper Pearson exact intervals. Disability improvement at Visit 2 and Visit 3 will also be presented and derived in the same way as described for Visit 4.

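### The 9HPT rule in SAP 14.3.1 and 14.4.1 runs backwards: on the SAP's reciprocal score, faster hands count as progression and slower hands as improvement

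*SAP*

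**What the plan says.** SAP 14.3.1 compares Visit 4 with Visit 3 and sets disability progression to Yes if any one of its EDSS, T25FW or 9HPT conditions is met. The 9HPT condition is a "20% increase in the 9HPT score (The two trials for each hand are averaged, converted to the reciprocals of the mean times" for each hand; the two reciprocals are then averaged. SAP 14.4.1 gives the matching condition for improvement: a "20% decrease in the 9HPT score (The two trials for each hand are averaged, converted to the reciprocals of the mean times", again with the two reciprocals averaged. Neither section converts the average back to seconds.

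The T25FW conditions in the same lists use the plain average of two trial times: longer is progression, shorter is improvement.

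The protocol is less specific. Section 8.2 asks for change "with a ≥20% minimum threshold change for T25FW and 9HPT" without giving a direction or a scale. Section 9.3 lists the collected variable as "9-HPT (time in seconds, optional". Section 9.7.3 warns: "As T25FW and 9-HPT are optional and will be performed if done as per routine practice, missing values may occur".

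The same derivation serves other time points. For progression: "Disability progression at Visit 1, Visit 2 and Visit 3 will also be presented and derived in the same way". For improvement: "Disability improvement at Visit 2 and Visit 3 will also be presented and derived in the same way as described for Visit 4".

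**The concern.** A time in seconds rises as hand function worsens; its reciprocal rises as hand function improves. The increase-for-progression wording suits the first scale, but the SAP computes the second. Followed literally, the rule reports a patient whose hands have slowed markedly as improved, and one whose hands have sped up as progressed.

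The following rest on this rule:

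- the main analyses of 6-month progression and improvement, and their results at earlier visits;
- the subgroups by prior DMD;
- the first two sensitivity analyses of each endpoint. In the second one for progression, only patients with all three tests are affected, because patients without all three end as Yes in any case;
- the disability tables and bar plots in the interim output list (SAP 18.2).

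Sensitivity analyses 3 and 4 of each endpoint use EDSS alone and are safe, as is the primary ARR endpoint. SAP 9 limits confirmatory testing to the primary outcome, but protocol section 8 names disability progression in the study's main aim.

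A second, smaller issue is the scale. Twenty percent of an averaged reciprocal is not twenty percent of time, and the gap depends on whether one hand or both change.

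**Working it through.** The plan gives no figure to reproduce here, so I applied the rule as written, taking the Visit 3 to Visit 4 comparison as given.

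**Inputs.** The score is from SAP 14.3.1 and 14.4.1: S = (1/tA + 1/tB)/2, where tA and tB are the mean times of the two hands. The thresholds are S up 20% for progression and S down 20% for improvement. Planned enrolment is 242 (protocol 9.5). All times and rates below are assumed.

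**Both hands change by the same factor f.** The change in S is 100 × (1/f − 1) percent, whatever the starting times.

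| Change in time | Change in S | SAP as written | 20% rule on seconds | SAP score, directions swapped |
|---|---|---|---|---|
| −25.0% | +33.3% | progression | improvement | improvement |
| −20.0% (25 to 20 s) | +25.0% | progression | improvement | improvement |
| −16.7% (24 to 20 s) | +20.0% | progression | neither | improvement |
| −10.0% | +11.1% | neither | neither | neither |
| +10.0% | −9.1% | neither | neither | neither |
| +20.0% (20 to 24 s) | −16.7% | neither | progression | neither |
| +25.0% (20 to 25 s) | −20.0% | improvement | progression | progression |
| +50.0% | −33.3% | improvement | progression | progression |

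Every change that reaches the SAP threshold is coded the wrong way round. Against a 20% change in time, the errors fall into four bands:

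1. At least 20% faster: coded progression, improvement missed; both endpoints wrong.
2. 16.7% to under 20% faster: coded progression; one endpoint wrong.
3. 20% to under 25% slower: progression missed; one endpoint wrong.
4. At least 25% slower: progression missed, coded improvement; both endpoints wrong.

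**Hands change unequally.**

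- 20/20 s to 20/28 s: mean time 20 to 24 s (+20.0%). S goes from 0.0500 to (1/20 + 1/28)/2 = 0.0429 (−14.3%).
- 20/30 s to 20/40 s: mean time 25 to 30 s (+20.0%). S goes from 0.0417 to 0.0375 (−10.0%).
- From 20/20 s with one hand slowing, S reaches −20% only when that hand takes 33.3 s (mean time +33.3%).

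So swapping the directions corrects the sign but does not reproduce a 20% change in time.

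**How many patients.** Let c be the share with a 9HPT at both visits, a the share of those at least 16.7% faster, b the share at least 20% slower, and u the share not already decided by EDSS or T25FW. Judged on seconds, wrong progression statuses = 242 × c × (a + b) × u. With a = b = 5% and u = 1:

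- c = 10%: 242 × 0.10 × 0.10 = 2.4
- c = 25%: 6.1
- c = 50%: 12.1
- c = 100%: 24.2

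With u = 0.5 these halve. For a = b from 2% to 10%, u from 0.5 to 1 and c from 10% to 100%, the range is 0.5 to 48.

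**Net effect on the percentage.** The bias is c × u × (a − b). With a = b it is zero: the overall percentage looks normal while individual statuses are wrong. With c = 50%, u = 1, a = 8% and b = 2%, the 9HPT adds 242 × 0.5 × 0.08 = 9.7 progressors instead of 242 × 0.5 × 0.02 = 2.4, an overstatement of 0.5 × 0.06 = 3.0 percentage points.

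**The case against.** The reversal itself has no good answer. One could suppose that a programmer would work in seconds, or that a harmonic mean time was meant, but the SAP spells out the reciprocal step twice and never undoes it. Code that follows the text is wrong, and code that ignores it departs from the plan.

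The stronger objections concern size and benchmark.

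- **Scale.** The protocol does not say that the 20% applies to seconds. Bands 2 and 3 are errors only if it does; a correctly signed reciprocal rule would also record no progression in band 3. This stands: the reversal is a demonstrated error, the scale an ambiguity.
- **Counts.** Completion and change rates are assumed throughout. Having everyone tested is unlikely for an optional test, and 242 is planned enrolment, before dropouts and before statuses set to missing because Visits 3 and 4 are under 24 weeks apart. The 3.0-point bias comes from choosing 8% against 2%. This stands too: the true effect could be negligible.
- **Importance.** The endpoints are secondary and reported with confidence intervals, without a planned test. An unaffected estimate is already specified: "A third sensitivity analysis will be performed using EDSS only for disability assessment derivation". The descriptive 9HPT results by visit might expose the contradiction. This limits the damage, but it does not justify leaving a rule that reports the opposite of what the test shows.

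**Conclusion.** The concern holds, and the correction is needed. As written, any 9HPT change that crosses the SAP threshold is counted in the wrong direction for both disability endpoints. This follows from the SAP text alone and depends on no assumption about starting times or rates.

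A patient's composite status goes wrong when the 9HPT is available at both visits, the change crosses a cut, and neither EDSS nor T25FW already decides. Patients whose 9HPT change stays inside the cuts are not misclassified by this rule. How many are affected cannot be known from the documents; the central scenario of about 2 to 24 of 242, and the wider range of 0.5 to 48, are illustrations judged on the seconds scale. Equal numbers speeding up and slowing down would leave the overall percentage unchanged, so a plausible-looking result would not be reassuring.

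**What to change.** Rewrite the 9HPT bullets in SAP 14.3.1 and 14.4.1 on the scale in which the protocol records the test: progression is a rise of at least 20% in 9HPT time, improvement a fall of at least 20%. State how the hands are combined, for example as the mean of the two hands' mean times. Write the threshold as at least 20%, to match the protocol.

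If the reciprocal score is kept, swap the two directions and state whether the 20% applies to the score or to time. Score cut-offs of −16.7% for progression and +25% for improvement match a 20% change in time only when both hands change by the same factor.

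Label the scale in the descriptive 9HPT tables as well, and rerun any interim disability tables and plots produced under the present rule. Make the change before database lock, so that the definition is not altered after final results are seen. The cost is two SAP bullets, the matching code and table labels, and those reruns; no new data are needed.
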